7.0 Data and Specimen Banking

7.1 N/A.

8.0 Genetic Analysis Information

8.1 N/A

9.0 Sharing of Results with Subjects

9.1 Parents or Guardians of students in Arm #2 will receive weekly text messages with updates on the students overall physical activity and previous weeks step count. Step and minutes of physical activity information from the Garmin data may also be shared with the PE teachers. Information will be aggregate and will not contain any identifiers.

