1.0 Study Summary

Study Title	Stay Active
Study Design	Experimental Intervention
Primary Objective	To compare the impact of two physical activity interventions on student's physical activity.
Secondary Objective(s)	
Research Intervention(s)/ Investigational Agent(s)	Two arms: Arm 1: classroom based physical activity Arm 2: classroom based physical activity plus family support for physical activity.
IND/IDE #	
Study Population	Up to 15 classrooms from Kansas City area elementary schools.
Sample Size	Up to 250 Students, 250 parent(s)/guardian(s), and 15 teachers
Study Duration for Individual Participants	1 semester (for about 4 months)
Study Specific Abbreviations/ Definitions	CBPA: classroom based physical activity

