4.0 Study Endpoints

- 4.1** The primary endpoints are daily step counts and daily physical activity minutes.
- 4.2** The secondary endpoints are parent and teacher perceptions.

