- Family Component: A newsletter, with supporting handouts and resources for the family to use, will be sent to parents or guardians once every two weeks over the semester and posted on the study website. The newsletters include physical activity information related to safety/protection, skills building, motivation, overcoming barriers, and goal setting and monitoring. The handouts include optional worksheets and physical activity tracking sheets to support families. As part of the program, children also receive a Garmin wearable physical activity monitor. Parents or guardians will receive text messages with behavior change messages based on the Garmin data. Text messages also contain links to website materials. Parents/Guardians of students who receive a Garmin will receive text reminders about wearing the device if no steps or minutes of physical activity are being detected.

Texts will be sent out using the Twilio platform.

Participants (both parent and child) will be asked to complete two surveys during the study. Surveys ask questions related to general demographics, household physical activity habits, and COVID-19 related questions. The first survey has been submitted in the SmartForm (Baseline Survey_Version_0.02), the second survey will be submitted later as an amendment, as it is still being developed.

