6.0 Procedures Involved

6.1 Data Collection Procedures

- Describe the method for identifying candidates for the study
 - School Recruitment: We will work with district contacts to identify schools and classrooms to participate. School staff will be provided an informational letter about the study.
 - Participant Recruitment: A recruitment flyer will be sent to families via their classroom teacher.
- Describe the procedure for obtaining data
 - Teachers will receive weekly emails containing a brief REDCap survey to complete.
 - Teachers will complete a post intervention survey (we will submit this later as an IRB amendment, as it is still being developed).

SHORT TITLE: Stay Active

- Teachers will complete a post intervention interview (we will submit this later as an IRB amendment, as it is still being developed).
- If the teacher withdraws from the study, their class will no longer be able to participate in the Arm #1 of the study.
- Parents or guardians will complete a pre- and- post intervention survey, with the options of on paper or over RedCap. The post intervention survey will be submitted later as an IRB amendment, as it is still being developed.
- Students in both arms will be asked to wear Garmin physical activity devices to provide physical activity information throughout the intervention. The Garmin is worn like a wristwatch. The device is small and non-intrusive. The Garmin device is a consumer wearable that will automatically detect and track activity such as walking, running, and cycling.
- Study staff will set up the Garmin account with an email address provided by the parent and a generic password. This information will be shared in the Participant Garmin Instructions sent in the mail along with the Garmin device. Study staff will not input any personal information, aside from the provided email address, while creating the Garmin account.
- Students can participate in the CBPA portion of the study without opting in to wearing the Garmin device. This participant will not be consented or assented but will still receive the classroom physical activity lessons via their classroom.
- Students who neither opt out or opt in to the study will be allowed to participate in the CBPA portion of the study. No personal information or data will be collected from these students.
- Any potential participant that opts out of the CBPA portion of the study will be told that they can watch, engage in a separate activity, or leave the session temporarily.

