17.0 Risks to Subjects

17.1 Classroom:

- The primary risk, albeit minimal, is the risk of loss of confidentiality. The use of video conferencing could result in a potential loss of privacy, but study staff will be using the schools video conferencing system to minimize this risk.

17.2 Participants:

- The risk to the child's comfort, albeit minimal, is the wearing of the device daily on their wrists.
- There is a risk to the participant of loss of privacy due to the Garmin being a consumer device that uploads data to Garmin servers.
- There is a slight risk of loss of privacy due to the use of Twilio as the text messaging platform.
- There is a slight risk of burden to the parents or guardians due to the text messaging frequency.

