20.5 Secure Storage of Data

- Garmin data will be obtained through the Garmin API. It will show each student's daily minutes of physical activity and step counts when participants were wearing the device. Participant also have access to this information through their Garmin Connect account. As part of the consent/assent process study staff will describe that information from the devices will be

collected through the Garmin API and that Garmin will have access to this information.

Garmin data are stored on Garmin servers and will be accessed by the research team via the Garmin web apps on CMH secure computers. Study staff will not provide Garmin access to participant names or any other PHI that would make a participant readily identifiable. Reports will be aggregated across the participants so no participant will be identifiable, and no identifiable data will be published or presented.

Online surveys will be managed in REDCap.

To protect the security of responses on hardcopy surveys, participants will complete a confidential survey that includes a participant identification number on the form. The participant ID#, rather than name, will be recorded on hardcopy surveys. A master list containing the names and associated IDs will be kept securely in REDCap. No one except the study team members will have access to this master list. Names and descriptions of participants will not be published or reported. All data will be stored without identifiers, and only participant number. Survey data are entered on Children's Mercy computers and will be stored in REDCap. Research team members are trained to not divulge participants' information in anyway.

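### Recorded activity depends on device wear; the non-wear reminder may reach only Arm 2, and the pre-post analysis has no wear check

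*Combined protocol and SAP*

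**What the plan says.** The stated primary objective (section 1.0) is "To compare the impact of two physical activity interventions" on student activity. Section 4.1 adds: "The primary endpoints are daily step counts and daily physical activity minutes". Section 20.5 says the Garmin data show "daily minutes of physical activity and step counts when participants were wearing the device". Section 6.1 says "Students in both arms will be asked to wear Garmin physical activity devices", for the length of the intervention.

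Three kinds of text message are described:

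- **Weekly feedback**, expressly for one arm (section 9.1): "Parents or Guardians of students in Arm #2 will receive weekly text messages with updates on the students overall physical activity".
- **Behaviour-change texts** driven by the Garmin data, listed in the Arm 2 Family Component (section 5.3).
- **Non-wear reminder**, in that same Arm 2 paragraph but addressed more widely: "Parents/Guardians of students who receive a Garmin will receive text reminders about wearing the device". It is triggered when no steps or activity minutes are detected.

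Section 5.3 also presents the device as an Arm 2 item: "As part of the program, children also receive a Garmin wearable physical activity monitor". The text-message burden listed in section 17.2 names no arm: "There is a slight risk of burden to the parents or guardians due to the text messaging frequency".

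Section 15.2 pays participants $25 for wear in the first week, and $25 for wear in the last week together with the final survey. Neither payment is limited to an arm. Sections 20.2 and 20.4 plan a between-group comparison of pre-to-post change by mixed model, with time nested in participants and participants in classrooms. They state no valid-day rule, treatment of zero-step days, report of wear by arm or wear-adjusted analysis.

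**The concern.** A recorded daily total reflects both how active the child was and how long the device was on. If wear differs between arms, the totals can differ even when activity does not.

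The reminder is the most direct route, because its purpose is to restore data capture. As section 5.3 is laid out, a study team could reasonably send it to Arm 2 families only. As it is worded, and given that both arms wear the device under section 6.1, the team could equally send it to everyone.

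A pre-post contrast removes a wear difference that is constant over the study. It does not remove one that opens up between the pre and post periods, because that falls into the arm-by-time contrast used to estimate the intervention effect. At stake is the interpretation of the trial's only primary comparison.

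**Working it through.** **1. Nothing to reproduce.** The documents give no wear figure, effect size, SD or power, and section 20.3 bases the sample size on resources. Every number below is therefore an illustration on assumed inputs.

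**2. Passages side by side on the reminder.**

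| Section | Points to Arm 2 only | Points to both arms |
|---|---|---|
| 5.3 | Reminder sits in the Family Component; the Garmin is listed as part of that program | Reminder is addressed to families of students given a Garmin |
| 6.1 | – | Both arms are asked to wear the device |
| 9.1 | – | Names Arm 2 when Arm 2 is meant |
| 17.2 | – | Text burden is not limited to an arm |

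No passage settles the question.

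**3. Longer wear within the day.** Assumptions:

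- no true effect, and equal wear at pre;
- S = 8,000 to 10,000 steps per 13-hour day, with an hourly rate S/13 that does not depend on hours worn;
- daily wear normal with mean 10 hours in Arm 1 and 10 + gap in Arm 2 at post, SD 2 to 4 hours, clipped to 0.1–14 hours.

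Spurious difference = (S/13) × (mean clipped hours in Arm 2 − mean clipped hours in Arm 1).

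- Lowest case (gap 0.25 h, SD 4, S = 8,000): 615.4 × (9.8823 − 9.6754) = 615.4 × 0.2069 = **+127** steps/day.
- Middle case (gap 0.5 h, SD 3, S = 9,000): 692.3 × (10.3201 − 9.8732) = 692.3 × 0.4469 = **+309** steps/day.
- Highest case (gap 1.0 h, SD 2, S = 10,000): 769.2 × (10.9414 − 9.9830) = 769.2 × 0.9584 = **+737** steps/day.

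**4. Whole days only.** If non-wear days are missing and every worn day is complete, each worn day records S in both arms and the spurious difference is **0**.

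**5. Why the sign is open.** Suppose non-wear days are missing, 60% of days are fully worn, and prompts add partial days of h hours making up a fraction q of all days. The change in the Arm 2 mean is (0.6S + q × S × h/13)/(0.6 + q) − S. With q = 0.05:

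- h = 8, S = 8,000: −237 steps/day;
- h = 4, S = 10,000: −533 steps/day.

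A successful reminder could therefore lower the Arm 2 mean.

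**6. What a valid-day rule removes.** Gap 1.0 h, S = 9,000, as in step 3:

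| SD of wear (h) | No rule | At least 8 h | Share left |
|---|---|---|---|
| 2 | +663 | +457 | 69% |
| 3 | +607 | +314 | 52% |
| 4 | +557 | +225 | 40% |

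A rule of at least 2,000 steps leaves +528 to +563 of the +607 at SD 3, which is 87% to 93%. This was simulated with 4,000,000 days per arm and a lognormal hourly rate with CV 0.5 or 0.3. Steps per worn hour, with no step rule, shows no arm difference, but only because step 3 assumes that rate is independent of hours worn.

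**The case against.** The best reply is that the documents show an ambiguity and an omission, not a bias. The reminder may always have been meant for both arms: its wording names no arm, whereas section 9.1 names Arm 2 when it means Arm 2. On that reading the most direct route disappears and the first remedy is a change of wording. The $25 payments are the same in both arms and reward wear in the first and last weeks, which are the natural pre and post periods. The study is a pilot sized on resources, so there is no power claim to upset and a short analysis section is unsurprising.

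Much of this stands. A reader might infer that the plan has no protection against unequal wear. The documents do not support that, because the payments are arm-neutral and the reminder may be common. A reader might also infer that Arm 2 results will be inflated. No passage says the feedback or behaviour-change texts alter wear, and step 5 of the working shows the sign could be negative. Larger upward figures follow if non-wear days are scored as zero, but section 20.5 describes data from worn time, so treating those days as missing is the more natural reading.

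What the reply does not answer is the analysis. The payments do not define how much wear counts, the pre and post windows are not tied to the paid weeks, and wear within a day can still differ. Pilot status does not remove a primary objective stated as a between-arm comparison.

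**Conclusion.** The point holds as a cheap improvement that should be made. It is well supported that the endpoints accrue only during wear, that the feedback texts are Arm 2 only, that the reminder's scope is unresolved between sections 5.3 and 6.1, and that section 20.4 states no analytic wear check. It is not shown that wear would differ, or that any difference would be material. Existing protection is partial rather than absent.

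Neither size nor direction can be derived from the documents. The range of +127 to +737 steps per day rests entirely on the assumptions in step 3 of the working, and the result is nil when worn days are complete and non-wear days are missing. Confidence is high that no wear check is stated and moderate that its absence would matter.

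**What to change.** 1. **Reconcile sections 5.3 and 6.1.** Move the non-wear reminder to the common procedures in 6.1 and send it to Garmin families in both arms with the same trigger and frequency. Keep only the feedback and behaviour-change texts in Arm 2. If both arms were always intended, this is a wording change.
2. **Section 20.4, handling of days.** Treat non-wear days as missing, not zero. Apply one valid-day rule identically in both arms, fixed before data are seen by arm. The exact threshold is the study team's choice.
3. **Section 20.4, reporting.** Report valid days by arm at pre and post, with wear hours if the Garmin data supply them. Add one sensitivity analysis, using either activity per worn hour or adjustment for wear time.
4. **State the limits.** Any valid-day rule, by hours or by steps, removes only part of a wear-hours difference. Section 20.5 lists only minutes and steps, so wear time may be unavailable; if it is, say so as a limitation.

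**Cost:** a few automated texts to Arm 1 families on the platform already in use, short edits to 5.3, 6.1 and 20.4, and one extra analysis. Some days will be excluded. Wear time is measured after randomisation, so adjusting for it belongs in a sensitivity analysis only, and the per-hour version assumes that activity rate is unrelated to hours worn.

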10.0 Study Timelines

	Aug 2020	Sep 2020	Oct 2020	Nov 2020	Dec 2020	Jan 2020	Feb 2020	Mar 2020
Recruit participants								
Collect data								
Conduct intervention								
Analyses								
Publication and presentation								

11.0 Inclusion and Exclusion Criteria

11.1

Inclusion Criteria

- *Classrooms*
 - Teacher of a 4th or 5th grade class in the Kansas City area.
 - English speaking only
- *Students*

- Any student in the selected classrooms
- A parent or guardian of the student that has a smartphone
- English speaking only

Exclusion Criteria

- Does not meet the required criteria above.

11.2 Indicate specifically whether you will include or exclude each of the following special populations:

- Adults unable to consent- EXCLUDE
- Individuals who are not yet adults (infants, children, teenagers) - INCLUDE
- Pregnant women – we will not be screening for pregnancy so there is potential that pregnant women will be participating.
- Prisoners – EXCLUDE
- Wards of the state - EXCLUDE

12.0 Vulnerable Populations

12.1 **Children:** P/A will be obtained from participants under the age of 18 and their parent/LAR. Research staff involved in the P/A process will review the HRP-416 CHECKLIST – Children to ensure sufficient information is provided during the P/A appointment with the child and their parent/LAR.

13.0 Local Number of Subjects

13.1 Up to 15 Kansas City school teachers and classrooms.

13.2 Up to 250 students (4th and 5th graders), 250 parent(s)/guardian(s), and 15 teachers

14.0 Screening and Recruitment Methods

14.1 Classrooms

- We will work with district contacts to identify schools and classrooms to participate.
- A study information letter will be sent out via multiple modes of communication to schools and teachers.
- Study staff will communicate with the leader in the district who has authority to approve the project. The leader then identifies the classrooms and relays what classrooms have been selected to study staff.

14.2 Participants

- A recruitment flyer will be sent out via multiple modes of communication to all families of 4th and 5th grade students in

classrooms of selected teachers that are participating. The recruitment flyer will be sent by the teacher.

- The recruitment flyer will describe the CBPA as all students in the classroom (even those who do not wear the Garmin device) will be able to participate in the CBPA if desired. The recruitment flyer will explain that such students/families can opt out of receiving the CBPA by contacting the study team or their teacher. These students will not complete any study assessments.
- The recruitment flyer will also describe the Garmin assessment portion of the study and the potential family content that half of the classrooms will be randomized. To enroll in the Garmin portion of the study participants will need to opt in by contacting the study team. Thus, these are the study participants who will be consented/assented and measured/assessed.
- Research staff will respond via email or telephone to inquiries generated by the recruitment email and flyer. The research team will go over the details of the study with potential participants over the phone or email. If a potential participant says they want to enroll in the study after receiving the study information, having any questions answered by the research team member, and being confirmed as eligible, the parent and child will be consented and assented over the phone. E-consent will then officially take place over the phone and REDCap. The participant will receive a copy of the P/A/C form and participant instructions by e-mail or in the mail.

14.3 We will have access to parent names, email addresses, and phone numbers prior to obtaining permission/assent. We are requesting a waiver of HIPAA authorization for recruitment purposes only. We will not retain any data from potential participants who do not enroll in the study.

15.0 Reimbursement, Payment and Tangible Property provided to subjects

15.1 Classroom teachers who complete the post intervention assessments will receive a Greenphire ClinCard in the amount of \$50.

15.2 Participants will receive up to \$50 for participating. The cash card will be issued at the end of the fall semester. \$25 will be given to participants who wear the Garmin device the first week of the study. Another \$25 will be given to participants who wear the device the last week of the study and complete the final survey, which is completed by the parent and child. In addition to the cash card, the participant will be able to keep the Garmin device at the end of the program, which is valued at \$80.

15.3 The research team will collect the required information (e.g. address and date of birth) for issuing compensation after P/A/C has been obtained during the P/A/C appointment. This information will be immediately entered into Greenphire by the research team and then shredded to protect confidentiality. Payment will be issued to the participant when they complete the study and complete the final survey.

15.4 If the participant chooses to withdraw at any point during the study, they will not be asked to return the Garmin device. They will be compensated for each portion of the study they complete.

16.0 Withdrawal of Subjects

16.1 Participants will be informed that they may withdraw from the study at any time by contacting a member of the research team.

16.2 Data collected from subjects prior to withdrawal will be retained for analysis. At the time subjects withdraw, no additional data will be collected from the subject.

17.0 Risks to Subjects

17.1 Classroom:

- The primary risk, albeit minimal, is the risk of loss of confidentiality. The use of video conferencing could result in a potential loss of privacy, but study staff will be using the schools video conferencing system to minimize this risk.

17.2 Participants:

- The risk to the child's comfort, albeit minimal, is the wearing of the device daily on their wrists.
- There is a risk to the participant of loss of privacy due to the Garmin being a consumer device that uploads data to Garmin servers.
- There is a slight risk of loss of privacy due to the use of Twilio as the text messaging platform.
- There is a slight risk of burden to the parents or guardians due to the text messaging frequency.

18.0 Potential Benefits to Subjects

18.1 Participants will benefit from resources and opportunities provided on how to be physically active during the COVID-19 pandemic.

18.2 Participants may experience health and developmental benefits from increasing their physical activity.

19.0 Investigator Assessment of Risk/Benefits Ratio: (IRB makes the final determination) *Based upon your response in Sections 17.0 and 18.0, please provide your assessment of risk and benefits in below table.*

Select as applicable:	Pediatric Risk Category:	
X	Category 1	Research not involving greater than minimal risk (45 CFR §46.404 and 21 CFR §50.51)
	Category 2	Research involving greater than minimal risk but presenting the prospect of direct benefit to the individual subjects. (45 CFR §46.405 and 21 CFR §50.52)
	Category 3	Research involving greater than minimal risk and no prospect of direct benefit to individual subjects, but likely to yield generalizable knowledge about the subject's disorder or condition. (45 CFR §46.406 and 21 CFR §50.53)
	Category 4	Research not otherwise approvable which presents an opportunity to understand, prevent, or alleviate a serious problem affecting the health or welfare of children. (45 CFR §46.407 and 21 CFR §50.54)
Select if applicable:	Adult Risk Category:	
X	Not Greater than Minimal Risk	
	Greater than Minimal Risk	

